6.11. Bioanalytical and Pharmacokinetic/Pharmacodynamic Methods

Observed ixekizumab serum concentrations will be summarized by treatment group, visits, and corresponding time when sampling occurred.

As appropriate, the PK and the exposure-response relationship between ixekizumab exposure and clinically important efficacy measures (for example, ASAS40 or ASAS20 at Week 16) may be explored using graphical methods and/or a modeling approach. Pharmacokinetic and/or exposure-response data from this study may be combined with existing PK and/or exposure-response data from other studies, if considered appropriate.

If a trend or statistically significant difference between the ixekizumab dose cohorts and/or the placebo cohort is noted in any safety endpoint, the exposure relationship for this endpoint may be explored graphically.

In addition, the potential impact of immunogenicity on ixekizumab exposure and/or efficacy responses may be evaluated by graphical assessments, as appropriate, to compare drug exposure or efficacy responses between anti-drug antibody (ADA) negative and ADA positive patients at corresponding visits, or before and after ADA development for patients who developed ADA. Both treatment-emergent only and all ADA positive/negative patients may be explored. A similar approach may be taken if patients become NAb positive. The effect of immunogenicity may be evaluated as a covariate in the population PK and exposure-response analyses, if applicable.

For further details, refer to the PK/PD analysis plan.

6.12. Safety Analyses

Safety will be assessed by summarizing and analyzing AEs, laboratory analytes, vital signs, QIDS-SR16, and C-SSRS. The duration of treatment exposure will also be summarized.

For **Period 2**, safety data will be summarized for the safety population. Treatment group comparisons will be performed on categorical safety data using Fisher's exact test as described in Section 6.1.1, continuous safety data will be analyzed by an ANCOVA model as described in Section 6.1.1.

For **Period 3**, safety data will be summarized for the Extended Treatment Period Population and no treatment group comparisons will be performed.

For Combined Periods 2 and 3, safety data will be summarized for the Safety Population who are initially randomized to Ixekizumab, and no treatment group comparisons will be performed. In addition, safety data on ixekizumab will be summarized for All Ixekizumab Exposures Safety Population who had at least 1 dose of Ixekizumab.

For **Period 4**, safety data will be summarized according to the treatment patients were on or prior to entering Post-Treatment Follow-up Period.

For safety analyses, the following baselines will be used:

- Treatment-emergent adverse events (TEAEs): baseline will be all results recorded during the baseline period (see Section 6.1 for definitions of the baseline period).
- Change from baseline to last observation and each scheduled postbaseline visit for laboratory and vital signs: baseline will be last non-missing assessment recorded during the baseline period (see Section 6.1 for definitions of the baseline period).
- Treatment-emergent abnormal laboratory and vital signs: baseline will be all results recorded during the baseline period (see Section 6.1 for definitions of the baseline period).
- Change from baseline to minimum or maximum: baseline will be all results recorded during the baseline period (see Section 6.1 for definitions of the baseline period).

6.12.1. Extent of Exposure

Duration of exposure to study drug will be summarized by treatment group for Safety Population during Period 2 and Extension Period Population for Period 3 using descriptive statistics.

Exposure for Safety Population who are randomized to ixekizumab at Week 0 and All Ixekizumab Exposures Safety Population during Combined Periods 2 and 3 will be provided.

A by-patient listing of exposure duration with number of active injections and total dose will be provided.

The duration of exposure will be calculated as:

$$\begin{aligned} \text{Duration of exposure (days)} \\ &= \text{Date of last visit (scheduled or unscheduled) in Treatment Period} \\ &\quad - \text{Date of first dose in Treatment Period} + 1 \end{aligned}$$

The number and percentage of patients in each of the following categories will be included in the summaries:

- >0, ≥7 days, ≥14 days, ≥30 days, ≥60 days, ≥90 days, ≥120 days (for Period 3, add ≥150 days, ≥183 days, ≥210 days, and ≥273 days). Note that patients may be included in more than 1 category.
- >0 to <7 days, ≥7 to <14 days, ≥14 to <30 days, ≥30 to <60 days, ≥60 to <90 days, ≥90 to <120 days, ≥120 days (for Period 3, change ≥120 days to ≥120 to <150 days, add ≥150 to <183 days, ≥183 to <210 days, ≥210 to <273 days, and ≥273 days).

The summaries will also include the following information:

- Total exposure in patient years, calculated as:

$$\begin{aligned} \text{Total exposure in patient years} \\ &= \frac{\text{Sum of duration of exposures for all patients in treatment group}}{365.25} \end{aligned}$$

- Mean and median total dose. Total dose (in mg) is calculated by the number of active injections taken during the treatment period multiplied by dose. For those randomized to ixekizumab 80 mg (Q2W or Q4W) or adalimumab (Q2W), the total dose (in mg) taken during Period 2 or 3 will be calculated as follows:

Total Period 2 or 3 dose for patients on ixekizumab 80 mg Q2W
= Total number of active injections (including loading doses, if any) received in Period 2 or 3
× 80

Total Period 2 or 3 dose for patients on ixekizumab 80 mg Q4W
= Total number of active injections (including loading doses, if any) received in Period 2 or 3
× 80

Total Period 2 dose for patients on adalimumab 40 mg (Q2W)
= Total number of active injections received in Period 2 × 40

- Total number of injections received will be derived using the response to the question “Was dose administered?” on the *Exposure as Collected* eCRF page and the actual dose description from IWRS study drug dispense dataset.

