**Table RHBV.3. Treatment Regimens from Week 16 to Week 50**

Initial Regimen		Dose Week 16 a	Dose Week 18 to Week 50 (Period 3)
	Total injections per patients	2 injections	1 injection Q2W
ixekizumab 80 mg Q2W	Treatment dose	1 ixekizumab 80 mg injection	1 ixekizumab 80 mg injection Q2W (Beginning at Week 18, Q2W)
	Injections to maintain blinding	1 placebo for ixekizumab injection	None
ixekizumab 80 mg Q4W	Treatment dose	1 ixekizumab 80 mg injection	1 ixekizumab 80 mg injection Q4W (Beginning at Week 20, Q4W)
	Injections to maintain blinding	1 placebo for ixekizumab injection	1 placebo for ixekizumab injection Q4W (Beginning at Week 18, Q4W)
adalimumab 40 mg Q2W (comparator)		rerandomized to ixekizumab 80 mg Q2W or ixekizumab 80 mg Q4W b	
	Treatment dose	None	ixekizumab 80 mg Q2W or ixekizumab 80 mg Q4W beginning at Week 20
	Injections to maintain blinding	2 placebo for ixekizumab injections	1 placebo injection at Week 18 only (ixekizumab 80 mg Q2W regimen) or 1 placebo for ixekizumab injection Q4W beginning at Week 18 (ixekizumab 80 mg Q4W regimen)
placebo		rerandomized to ixekizumab 80 mg Q2W or ixekizumab 80 mg Q4W	
	Treatment dose	2 ixekizumab 80 mg injections (starting dose)	ixekizumab 80 mg Q2W beginning at Week 18 or ixekizumab 80 mg Q4W beginning at Week 20
	Injections to maintain blinding	None	None (ixekizumab 80 mg Q2W regimen) or 1 placebo for ixekizumab injection Q4W beginning at Week 18 (ixekizumab 80 mg Q4W regimen)

a Patients on placebo will receive a starting dose of 160 mg ixekizumab (2 ixekizumab 80 mg injections) at Week 16. All other patients will receive placebo injections as needed to maintain blinding.

b Patients assigned to the adalimumab treatment group at Week 0 will be re-randomized to an ixekizumab regimen at Week 16, but they will not receive an ixekizumab injection at Week 16. These patients will receive 2 placebo for ixekizumab injections at Week 16 to maintain the blind. Patients will receive their first ixekizumab dose (a single 80 mg injection) at Week 20, after the wash out period is complete. Patients will then maintain the ixekizumab regimen they were re-randomized to (ixekizumab 80 mg Q2W or ixekizumab 80 mg Q4W), with placebo injections as needed to maintain blinding.

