6.1.2. General Considerations for Analyses during the Extended Treatment Period (Period 3)

Unless otherwise specified, Period 3 starts at the first injection of study treatment at Week 16 (Visit 8) and ends on the date of Week 52 (Visit 15) or the ETV (between Weeks 16 and 52).

For the efficacy and health outcome analyses, baseline is defined as the last available value before the first injection in Period 2 and, in most cases, will be the value recorded at Week 0 (Visit 2).

Unless otherwise specified, for the safety analyses during Period 3, baseline is defined as the last available value before first injection of ixekizumab in Period 3. In most cases, this will be the measure recorded at Week 16 (Visit 8). For adalimumab patients in Period 2 who are randomized to ixekizumab during Period 3, this will be the measure recorded at Week 20 (Visit 9). For treatment-emergent adverse events (TEAEs), baseline is the events ongoing just prior to the first injection of the study drug injection at Week 16 (for placebo and ixekizumab patients) or Week 20 (for adalimumab patients who are randomized to ixekizumab during Period 3).

The number and percentage of patients having categorical efficacy response (for example, ASAS40) will be summarized by treatment group for all scheduled visits (NRI), including Week 52 (Visit 15) during Period 3.

In addition, the number and percentage of patients achieving response on ASAS20 for those who did not achieve response at Week 16, and the number and percentage of patients maintaining response for those who achieved response at Week 16, will be summarized by treatment group for all scheduled visits (NRI), including Week 52 (Visit 15) during Period 3. Similar summary will be provided for ASAS40.

Each continuous efficacy and health outcome score and change from baseline (or percent improvement) will be summarized by treatment group at all scheduled visits, including Week 52 (Visit 15) using descriptive statistics (n, mean, SD, median, minimum and maximum). Missing data will be imputed using mBOCF method (Section 6.3.2).

The categorical safety measures will be summarized with incidence rates. The mean change of the continuous safety measures will be summarized at all scheduled visits.

6.1.3. General Considerations for Analyses during Combined Blinded Treatment Dosing Period and Extended Treatment Period (Combined Periods 2 and 3)

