All Ixekizumab Exposures Safety Population: Safety analyses for combined Blinded Treatment Dosing Period and Extended Treatment Period will be conducted on the All Ixekizumab Exposures Safety Population, defined as all patients who received at least one dose of ixekizumab during the study. For each patient, only periods in which ixekizumab is administered are included.

Follow-Up Population: Safety analyses for Period 4 will be conducted on the Follow-Up Population, defined as all randomized patients who received at least 1 dose of study treatment and have entered the Period 4. Patients will be analyzed according to the treatment they received before entering the Follow-up Period.

[Table RHBV.6.1](#) summarizes the major analysis purposes intended for each analysis population.

[Table RHBV.6.2](#) describes the treatment groups and the comparisons for each study period and analysis population.

Table RHBV.6.1. Major Analysis Purposes Intended for Each Analysis Population

	ITT Population	Per-Protocol Set	Safety Population	Extended Treatment Period Population	Adalimumab Washout Population	ITT (Safety) Population Who are Initially Randomized to Ixekizumab at Week 0	All Ixekizumab Exposures Safety Population	Follow-Up Population
Disposition	For Period 2			For Period 3				For Period 4
Baseline Characteristics ^a	For baseline			For baseline				
Treatment Compliance			For Period 2	For Period 3				
Concomitant Medication	For Period 2			For Period 3				
Protocol Deviation	For Period 2			For Period 3				
Exposure			For Period 2	For Period 3		For Combined Periods 2 and 3	For Periods 2 and 3, on ixekizumab treatment only	
Efficacy and Health Outcome Analyses	For Period 2. For Period 4, ASAS40 only	For ASAS40, ASAS20 in Period 2		For Period 3		For primary and major secondary objectives, and selective measures in Combined Periods 2 and 3		
Safety Analyses			For Period 2	For Period 3	TEAE for Week 16 to Week 20	For Combined Periods 2 and 3	For Periods 2 and 3, on ixekizumab treatment only	For Period 4
Subgroup Analyses on Efficacy	For Period 2							
Subgroup Analyses on Safety Outcome			For Period 2					

Abbreviations: ASAS = Assessment of Spondyloarthritis International Society; ITT = intent-to-treat; TEAE = treatment-emergent adverse event.

^a including patient demographics and other baseline characteristics, historical illness, preexisting conditions, prespecified medical history, previous therapy.

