	MASES score = 0 (similarly SPARCC = 0)	Logistic regression analysis with NRI; Fisher's exact test with NRI	ITT Population with Baseline MASES >0 (or SPARCC >0)	IXE80Q2W & IXE80Q4W vs. placebo at Week 16 and all other postbaseline visits in Period 2	Other secondary efficacy analyses (Section 6.10.4).
		Descriptive statistics of MASES = 0 (or SPARCC=0)	Extended Treatment Period Population with Baseline MASES >0 (or SPARCC >0)	No treatment group comparisons during Period 3	Other secondary efficacy analyses (Section 6.10.4).
Peripheral Arthritis	TJC and SJC change from baseline	MMRM	ITT Population with baseline TJC >0 (or SJC >0)	IXE80Q2W & IXE80Q4W vs. placebo at Week 16 and all other postbaseline visits in Period 2	Other secondary efficacy analyses (Section 6.10.4).
		ANCOVA with mBOCF	ITT Population with baseline TJC >0 (or SJC >0)	IXE80Q2W & IXE80Q4W vs. placebo at Week 16 and all other postbaseline visits in Period 2	Other secondary efficacy analyses (Section 6.10.4).
		Descriptive statistics of change from baseline	Extended Treatment Period Population with baseline TJC >0 (or SJC >0)	No treatment group comparisons during Period 3	Other secondary efficacy analyses (Section 6.10.4).
	TJC = 0 (similarly, SJC = 0)	Logistic regression analysis with NRI; Fisher's exact test with NRI	ITT Population with Baseline TJC >0 (or SJC >0)	IXE80Q2W & IXE80Q4W vs. placebo at Week 16 and all other postbaseline visits in Period 2	Other secondary efficacy analyses (Section 6.10.4).

Measure	Variable	Analysis Method (Sections 6.1, 6.3)	Population (Section 6.1.5)	Comparison/Time Point	Analysis Type
		Descriptive statistics of TJC = 0 (or SJC =0)	Extended Treatment Period Population with Baseline TJC >0 (or SJC >0)	No treatment group comparisons during Period 3	Other secondary efficacy analyses (Section 6.10.4).
Anterior uveitis	Crude and exposure-adjusted incidence rates for patients with anterior uveitis	Fisher’s exact test and Poisson regression	ITT Population	IXE80Q2W & IXE80Q4W vs. placebo during Period 2	Other secondary efficacy analyses (Section 6.10.4).
		Descriptive statistics	Extended Treatment Period Population	No treatment group comparisons during Period 3	Other secondary efficacy analyses (Section 6.10.4).
		Descriptive statistics	ITT Population Who are Initially Randomized to Ixekizumab	No treatment group comparisons during Combined Periods 2 and 3	Other secondary efficacy analyses (Section 6.10.4).

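### Period 3 exposure for adalimumab-to-ixekizumab switchers includes 28 days of placebo washout and does not match their Week 20 safety baseline

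*SAP*

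**What the plan says.** **Exposure.** SAP 6.12.1 gives one duration formula for every period and population: date of last visit in the period, minus "Date of first dose in Treatment Period", plus 1. Patient-years are the sum of these durations divided by 365.25. Total dose, in the same section, counts active injections only.

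**Start of Period 3.** SAP 6.1.2: "Unless otherwise specified, Period 3 starts at the first injection of study treatment at Week 16 (Visit 8".

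**What switchers receive.** Protocol Table RHBV.3, footnote b: "These patients will receive 2 placebo for ixekizumab injections at Week 16 to maintain the blind". It continues: "Patients will receive their first ixekizumab dose (a single 80 mg injection) at Week 20, after the wash out period is complete". SAP 6.1.5 itself describes the washout injections as placebo doses, so the word dose in the exposure formula does not exclude them.

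**Where switchers are reset to Week 20.** SAP 6.1.2 puts the Period 3 safety baseline at Visit 9 and the treatment-emergent adverse event (TEAE) baseline at "Week 20 (for adalimumab patients who are randomized to ixekizumab during Period 3". SAP 6.1.3 uses Visit 9 for the All Ixekizumab Exposures Safety Population, and Table RHBV.6.10 uses Week 20 for immunogenicity. Week 16 to 20 TEAEs have their own Adalimumab Washout Population in 6.1.5.

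**Person-time rates.** SAP 6.1.3 plans exposure-adjusted adverse event rates in the All Ixekizumab Exposures population, described in 6.1.5 with the limit "For each patient, only periods in which ixekizumab is administered are included". Table RHBV.6.5 plans "Crude and exposure-adjusted incidence rates for patients with anterior uveitis" and summarizes them in the Extended Treatment Period Population among others.

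**The concern.** The SAP moves the adalimumab switchers to Week 20 for baselines, TEAEs and immunogenicity, but has no matching rule for exposure. Read literally, four weeks in which these patients receive only placebo, shortly after their last adalimumab dose, count as exposure in a period whose summaries are labelled by ixekizumab regimen. Table RHBV.6.2 also pools switchers into the Total Ixekizumab 80 mg Q4W, Total Ixekizumab 80 mg Q2W and overall Total columns.

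At stake are the Period 3 patient-years and any rate that uses them as denominator. If events are counted from Week 20 and person-time from Week 16, the rate after switching comes out too low. Even without a rate, dose and duration for switchers in one exposure summary cover different windows.

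The TEAE start is itself inconsistent. SAP 6.12.2 classifies events from the first dose in the treatment period, the same anchor as the exposure formula, while 6.1.2 says Week 20. Under 6.12.2, washout events could count as Period 3 TEAEs and also appear in the Adalimumab Washout Population.

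**Working it through.** **Inputs.** Study days from the protocol's Schedule of Activities: Week 16 = day 112 (±4), Week 20 = day 140 (±4), Week 44 = day 308, Week 52 = day 364 (±7). Allocation 1:1:1:1 with about 320 patients (SAP 5.3), so 80 per arm. Full retention is my assumption.

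**The plan's own Period 3 figures.** Length: (364 − 112)/7 = 36 weeks, as stated. Injections for a completer: 2 at Week 16 plus 17 from Week 18 to Week 50 = 19, as stated in SAP 6.8. The plan gives no exposure duration for switchers.

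**One switcher completing Week 52.**
- From Week 16: 364 − 112 + 1 = 253 days.
- From first ixekizumab at Week 20: 364 − 140 + 1 = 225 days.
- Excess: 28 days; 253/225 = 1.124, or +12.4%.
- A rate with events from Week 20 and time from Week 16 is multiplied by 225/253 = 0.889, so it is 28/253 = 11.1% too low.
- Range over the visit windows: 20/256 = 7.8% to 36/250 = 14.4%.

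**A switcher stopping at Week 44.** 308 − 112 + 1 = 197 days against 308 − 140 + 1 = 169; 28/197 = 14.2%. The duration band in 6.12.1 changes from ≥150 to <183 days to ≥183 to <210 days. For a Week 52 completer, 253 and 225 both fall in ≥210 to <273 days, so the band does not change.

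**80 completing switchers.** 80 × 253/365.25 = 55.4 patient-years against 80 × 225/365.25 = 49.3.

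**Pooled Period 3.** Excess 80 × 28 = 2,240 days. Time from Week 16 for all: 320 × 253 = 80,960 days. 2,240/80,960 = 2.8%.

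**All Ixekizumab Exposures, if Week 16 were used for switchers.** 160 × 365 + 80 × 253 + 80 × 253 = 98,880 days; 2,240/98,880 = 2.3%.

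**Which outputs the excess can reach.**

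| Output | Effect |
|---|---|
| Period 3 duration and patient-years (6.12.1) | Affected under the written rule |
| Period 3 adverse event summaries (6.12.2) | Numbers and percentages of patients; unaffected |
| Period 3 anterior uveitis rate (Table RHBV.6.5) | About 11% low in completing switchers if events count from Week 20 and time from Week 16; event start not stated |
| All Ixekizumab Exposures rates (6.1.3) | 2.3% pooled, only if the included periods mean all of Period 3 |

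**The case against.** A reader might infer that ixekizumab event rates in switchers are in general diluted by about 11%, in the drug's favour. The documents do not support that, for four reasons:

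- The main Period 3 adverse event results are percentages of patients, which person-time cannot change.
- The exposure-adjusted adverse event rates in 6.1.3 belong to a population limited to ixekizumab periods, with a Visit 9 baseline for switchers and a label in Table RHBV.6.2 restricting it to time on ixekizumab. That points to Week 20, although no derivation says so and the only duration formula is the one in 6.12.1.
- Uveitis is an efficacy outcome identified by preferred term. If its events are counted over Period 3 from Week 16, numerator and denominator cover the same time and nothing is diluted.
- Because 6.12.2 and 6.1.2 disagree on the TEAE start, a mismatch of events and time is not certain even for TEAEs.

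It can also be said that 6.12.1 summarizes exposure to study drug, which may include placebo, that switchers have their own columns, and that Period 3 has no between-group comparisons. These points limit the harm, and completers do stay in the same duration band. They do not remove the problem: the 28 days also enter the pooled ixekizumab columns, and the section gives switchers a duration from Week 16 beside a dose that can start only at Week 20.

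**Conclusion.** Wrong as written, with limited reach. The written rule adds 28 days of placebo washout to the Period 3 exposure of a switcher who follows the visit schedule: 253 against 225 days for a completer (+12.4%), and about 2.8% of pooled Period 3 patient-years with 80 per arm and full retention. The Extended Treatment Period Population requires at least one ixekizumab dose in Period 3, so every switcher in it carries this excess, and the relative error is larger for those who stop early.

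The 11.1% is a ratio of two exposure durations. It becomes the error of an event rate only where person-time starts at Week 16 and events at Week 20. The plan leaves that possible for the Period 3 uveitis rate, and for the all-ixekizumab rates only under the less natural reading of the included periods. Efficacy inference, Period 2 safety comparisons and Period 3 adverse event percentages are not touched.

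**What to change.** 1. In SAP 6.12.1, add that for patients moved from adalimumab to ixekizumab, exposure in Period 3 and in the All Ixekizumab Exposures Safety Population is the date of last visit minus the date of first ixekizumab injection, plus 1.
2. State that every exposure-adjusted rate, including anterior uveitis in Table RHBV.6.5, uses this same start date for events and for person-time in switchers.
3. In SAP 6.12.2, align the TEAE start for switchers with the Week 20 baseline in 6.1.2, so that Week 16 to 20 events appear only in the Adalimumab Washout Population.

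The cost is one sentence in 6.12.1, short matching edits elsewhere and a derivation change. No new data are needed: 6.12.1 already draws on the exposure eCRF page and the dispensing records, which identify the first active injection. Trial conduct does not change.

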6.12.2. Adverse Events

Adverse events (AEs) will be classified based upon the latest version of the MedDRA. Adverse events will be recorded at every study visit. Any condition starting on or after the date of informed consent will be considered an AE. Any preexisting condition which worsens in severity on or after the date of informed consent will be considered and recorded as an AE on the *Adverse Event (AE)* eCRF page from the date of worsening onwards.

A treatment-emergent adverse event (TEAE) is defined as an event that first occurred or worsened in severity after baseline and on or prior to the date of the last visit within the defined treatment period. Both the date/time of the event and the date/time of the dose (that is, injection) are considered when determining TEAEs. Treatment-emergent AEs will be assigned to the study period to which it's considered treatment-emergent:

- The MedDRA lowest level term (LLT) will be used when classifying AEs as treatment-emergent.
- The maximum severity recorded for each LLT prior to the first dose date/time in the treatment Period will be used as the pre-treatment severity for that LLT. If an event during the baseline period has missing severity, and the event persists during the treatment period, then it will be considered as treatment-emergent, regardless of the postbaseline level of severity. Events with a missing severity during the treatment period will be considered treatment-emergent.
- AEs with a particular LLT will be classified as treatment-emergent if they first start on or after the first dose date/time in the treatment period (ie, a patient has no preexisting conditions with that lowest level term), or if the severity is greater than the pre-treatment severity for that lowest level term. If a partial AE start date/time is present, the date/time will be compared as far as possible to the treatment start date/time in order to determine whether the event is treatment-emergent or not. If there is any doubt, the event will be flagged as treatment-emergent.

A follow-up emergent adverse event (FEAE) is defined as an event that first occurred or worsened in severity after the date of Visit 15 (that is, Week 52) or the ETV:

- The MedDRA LLT will be used when classifying AEs as follow-up emergent.
- For AEs that are ongoing at the date of Visit 15 or ETV, the maximum severity recorded for each LLT on or prior to the date of Visit 15 or ETV will be used as the follow-up baseline severity for that LLT.

If a partial or completely missing AE start date/time or end date/time is present the following imputation rules will be utilized in the analysis:

- For the start date:
 - If year, month, and day are missing, then use the earlier of the patient's first visit date or the consent date.
 - If either month or month and day are missing, then use January 1.
 - If only day is missing, impute the first day of the month.
- For the start time:
 - Impute as 23:59
- For the end date:
 - If year, month, and day are missing, then use the patient's last visit date in the follow-up period.
 - If either month or month and day are missing, then use December 31.
 - If only day is missing, then use the last day of the month.
 - The imputed date will not be beyond the patient's last visit date in the follow-up period.
- For the end time:
 - Impute as 23:59.
- If there is any doubt, the event will be flagged as treatment-emergent or follow-up emergent according the corresponding study period. If a follow-up emergent event was already counted as treatment-emergent during the prior treatment period, it will not be counted as a follow-up emergent event.

Adverse events and TEAEs will be summarized for the following study periods and analysis populations, treatment comparisons between treatment groups in Period 2 will be conducted using a Fisher's exact test:

- Period 2 (Safety Population)
- Period 3 (Extended Treatment Period Population)
- Combined Periods 2 and 3 (Safety Population who are randomized to ixekizumab at Week 0)
- Combined Periods 2 and 3 on ixekizumab treatment only (All Ixekizumab Exposures Safety Population)

The following summaries/analyses will be performed for all the populations above:

- An overall summary of AEs including the number and percentage of patients who experienced TEAE, TEAE by maximum severity, death, SAE, TEAE possibly related to study treatment, discontinuations from the treatment due to an AE, and TEAEs of special interest.

The following summaries will be provided for selective populations above:

- TEAE by system organ class (SOC) and preferred term (PT).
- TEAE by PT.
- TEAE by maximum severity, SOC, and PT.

Follow-up emergent adverse events will be summarized for the Follow-Up Population for Period 4:

- FEAE by PT.

In general, for all AE-related summaries, the number and percentage of patients experiencing the events will be presented by treatment group. In general, events will be ordered by decreasing frequency in the total ixekizumab group, followed in the order of ixekizumab Q2W, ixekizumab Q4W, adalimumab Q4W, and placebo (when applicable) group, within SOC and/or PT for sorting. For events that are gender-specific (as defined by MedDRA), the denominator and computation of the percentage will include only patients from the given gender.

A by-patient listing of all AEs will be provided.

